4.2 Perioperative management after hospitalization

4.2.1 Preoperative management: After admission, complete the following examinations: routine blood tests, liver and kidney function tests, electrolyte tests, coagulation function tests, thyroid function tests, CRP tests, procalcitonin (optional), serum β -HCG, anti-Müllerian hormone tests, pre-transfusion examinations, routine vaginal discharge tests, HPV/TCT tests, electrocardiogram, chest X-ray, and 3D color Doppler ultrasound of the uterus and bilateral adnexa. Patients must fast and abstain from drinking after midnight the night before surgery and sign a consent form.

routine vaginal discharge tests, HPV /TCT tests, and 3D color Doppler ultrasound have already been completed at the outpatient clinic and meet the requirements, there is no need to repeat these tests during hospitalization.

4.2.2 Surgical Procedure: Generally, intravenous general anesthesia is used

(with possible laryngeal mask airway support). (In special cases, local anesthesia, epidural anesthesia, or endotracheal intubation anesthesia may be chosen) . The patient is placed in the lithotomy position. If the anesthesia is satisfactory, normal saline is used for distension, and the distension pressure is maintained at 100-120 mmHg. It is recommended to use a diagnostic and therapeutic endoscope with an outer diameter < 5 mm (the specific type of endoscope and instruments used should be recorded) inserted through the cervix into the uterine cavity to determine the intrauterine condition: location and size of residual tissue, relationship to the uterine wall, whether the fallopian tube openings are visible, presence of adhesions in the uterine cavity, endometrial condition, etc. Then, the uterine depth is determined . (Under ultrasound monitoring) The cervix is dilated sequentially with dilators to size 8-10 (depending on the outer diameter of the hysteroscope used; hysteroscopic electrocautery is not recommended). Depending on the size of the pregnancy tissue , a 7mm outer diameter hysteroscope with 3mm diameter instruments is selected (for pregnancy tissue with a maximum diameter less than 10mm) or approximately 9mm outer diameter instruments with 4mm diameter instruments. The hysteroscope is then re-entered into the uterine cavity. It is recommended to use double-jointed spoon-shaped forceps under direct vision to remove any remaining tissue (refer to the demonstration surgery video for specific techniques). Suction and curettage methods should be avoided ; ultrasound-guided clamping with ovum forceps may be used appropriately. If a uterine septum or intrauterine adhesions are found during the procedure, they will not be addressed simultaneously if they do not affect the treatment of the remaining pregnancy tissue. For patients with pre-existing intrauterine adhesions, the location and nature of the adhesions should be described and recorded in detail during the procedure. The surgery should be performed by a physician with extensive experience in hysteroscopic procedures, with ultrasound or, if necessary, laparoscopic monitoring during the procedure to prevent uterine perforation. For patients with large surgical wounds, poor uterine contraction, and significant bleeding, slow intravenous infusion of oxytocin (100ml NS + 20U) or bimanual uterine massage can be used to promote uterine contraction and achieve hemostasis. If uncontrollable bleeding occurs, uterine artery embolization or even hysterectomy should be considered for hemostasis. If uterine perforation occurs during surgery, the operation should be terminated and the patient closely monitored; laparotomy or laparoscopic repair may be necessary. If a long operation is anticipated, a small dose of diuretic can be administered in advance and recorded. During surgery, endometrial damage should be minimized, and the distension pressure should be adjusted to the lowest possible level to reduce the absorption of distension fluid . The intake and output of distension fluid (a water intoxication detection instrument is preferable; refer to instruments developed by Hunan Comeson Company) and urine output should be recorded. Vital signs and blood oxygen saturation should be monitored, and blood gas analysis should be performed if necessary to prevent acute left heart failure .

All surgeons are gynecologists with extensive experience in hysteroscopic surgery who have received standardized training . **The following key points should be recorded during the procedure:** uterine depth; location and size of the pregnancy

tissue; operative time (from the start of uterine distension and insertion of the endoscope to its withdrawal); intraoperative blood loss (a routine blood test is recommended on the first postoperative day) ; whether there is any retained pregnancy tissue after the procedure; clarity of the surgical field; volume of distension fluid intake and output; whether there is a decrease in blood oxygen saturation; and whether complications such as uterine perforation, acute left heart failure, or gas embolism occur.

Note: 1) Hysteroscopic resection with a cold knife is recommended for removal of the pregnancy tissue. For surgical techniques, please refer to the surgical video. Link: https://pan.baidu.com/s/1F4RE6_g-gNtXsrhTs2B2UQ?pwd=1234

Extraction code: 1234.

Research institutions may choose ultrasound-guided curettage, micro-cold knife technique , intrauterine tissue excision system , or electrosurgical resection, depending on their own conditions, and should record the surgical method and instruments used.

2) If the surgical field is obstructed due to massive bleeding or other reasons, it is not essential to remove the pregnancy tissue. The primary goal is to ensure surgical safety and protect the endometrium. The procedure can be performed in stages.

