Hysteroscopic electrosurgical resection of pregnancy has a short operation time and less intraoperative bleeding. Direct visualization during the operation can avoid extensive curettage of the endometrium and significantly reduce complications such as incomplete curettage. For patients with uterine malformations, it can avoid blind curettage that misses part of the uterine cavity and leads to incomplete curettage, and can also treat uterine malformations simultaneously under hysteroscopy. However, the electrosurgical ring brings thermal radiation damage during treatment, which can easily damage the surrounding endometrial tissue, increase the risk of intrauterine adhesions, and in severe cases, damage the basement membrane or even the deep myometrium, leading to abnormal placental implantation in subsequent pregnancies [17].

Hysteroscopic cold knife removal of pregnancy tissue has no electrothermal damage, which is beneficial to protect the endometrium and reduce the risk of intrauterine adhesions and infertility after curettage. It is increasingly widely recognized [18]. Literature [19] compared the treatment of intrauterine diseases with electrocautery system and cold knife system and found that the latter reduced the incidence of intrauterine adhesions by 90% after surgery and could effectively avoid damage to the surrounding endometrial tissue by electroradiation. At present, the application of giant cold knife instruments is becoming more and more widespread. For example, the 4mm (i.e. 12 Fr) spoon forceps can directly remove residual tissue under vision, which has a great advantage over traditional micro forceps. The hysteroscopic shaving system uses a blunt head and side window operation to remove lesion fragments while removing lesions, avoiding repeated entry and exit from the uterine cavity. Its operation time is significantly shorter than that of the electrocautery group,

and the incidence of serious complications such as uterine perforation and massive bleeding is significantly reduced. At the same time, it avoids electrothermal radiation damage and significantly reduces intrauterine adhesions. However, it is important to emphasize the correct use method when using it, especially to avoid damage caused by excessive cutting of the endometrium.

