IV. Research Design

1. Research Subjects

who were diagnosed with retained products of pregnancy by ultrasound at outpatient clinics of various research units between June 2022 and June 2024, and who met the inclusion criteria but did not meet the exclusion criteria, were all enrolled consecutively.

Inclusion criteria: age 18-45 years, clinical diagnosis of retained products of conception, and ultrasound showing a lesion with a maximum diameter ≥ 0.5 cm.

Exclusion criteria: 1) Active bleeding requiring immediate surgical intervention; 2) Significant infection; 3) Severe organ dysfunction, including coagulation disorders.

Note: Patients with cervical tissue impacted in the cervical canal who have undergone clamping treatment and do not meet the exclusion

criteria can be included in this study;

2. Grouping

Because there is currently no unified treatment plan for retained products of pregnancy in uterus, the timing of active surgical evacuation versus expectant management until the planned surgery remains controversial, and the optimal timing for surgical evacuation is not uniform. In clinical practice, physicians, based on fully informed consent, choose active surgical treatment or expectant management according to the patient's wishes, and perform surgery when necessary. This study does not interfere with patient treatment; it only designs and collects relevant data in advance. No additional examinations or tests are performed on patients during the study process, and all procedures are conducted according to standard clinical practice. After treatment, patients are divided into an active surgical group and an expectant management group based on their chosen treatment plan, and data are statistically analyzed.

3. Sample size and allocation

The sample size was determined based on the incidence of intrauterine adhesions, the primary outcome measure. According to previous research results, the intrauterine adhesion rate in the expected group was 5.38%, and the intrauterine adhesion rate in the patients undergoing active surgery was 14.29%. The Type I error was 0.05, the power was 90%, and the sample size was calculated using PASS to obtain a total of 460 cases. Based on a 20% follow-up dropout rate, the sample size was calculated to be 576 cases. It is expected that 600 cases will be included, with 120 cases from the lead institution and an average of 40 cases from the other 12 research institutions.

4. Research Process

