5.2 Preoperative data on retained products of pregnancy: gestational age at termination; time of termination; serum β -HCG; imaging data (including ultrasound and MRI: uterine size, distance from the internal cervical os to the fundus, location of the retained products of pregnancy, maximum diameter, blood flow, presence of arteriovenous fistula (blood flow grade 1-6 in the retained products of pregnancy and surrounding uterine wall on color Doppler ultrasound), presence of placenta accreta, presence of intrauterine adhesions, uterine septum, uterine fibroids, adenomyosis. For the expectant management group, complete blood count, serum β -HCG, CRP, and ultrasound data from each follow-up examination should be collected.

5.3 Preoperative routine examination data : routine vaginal discharge test, HPV/TCT, complete blood count, liver and kidney function tests, electrolytes, coagulation function tests, thyroid function tests, serum β -HCG, anti-Müllerian hormone test, pre-transfusion examination, electrocardiogram, chest X-ray, 3D color Doppler ultrasound of the uterus and bilateral adnexa, and other relevant examinations. If a 3D ultrasound has been completed within one week in the outpatient clinic, it does not need to be repeated during hospitalization.

5.4 Surgical data: Date of surgery; depth of uterus; location and size of the gestational sac; operation time (from the start of the distension procedure to the withdrawal of the endoscope); amount of intraoperative blood loss; whether there is any retained gestational sac after surgery; clarity of the surgical field; volume of distension fluid in and out; whether there is a decrease in blood oxygen saturation;

whether complications such as uterine perforation, acute left heart failure, or gas embolism occur.

5.5 Postoperative follow-up data: serum β -HCG, complete blood count, CRP, procalcitonin (not required), ultrasound to check for retained products of conception, and if so, record the maximum diameter of the retained products.

5.6 Three months after treatment , outpatient follow-up data will be collected, including menstrual flow, ultrasound findings of intrauterine adhesions, endometrial condition, whether intrauterine adhesion surgery was performed, and intrauterine adhesion score.

5.7 Pregnancy outcome data collection: pregnancy rate after 1 year of trying to conceive ; miscarriage rate, premature birth rate, full-term birth rate, stillbirth rate, and stillbirth rate in subsequent pregnancies.

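### Section 4.2.2 both discourages and permits curettage and electrosurgery, the 5.4 data list omits surgical method, and the unadjusted adhesion comparison could therefore be biased by an unknown amount

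*Protocol*

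**What the plan says.** The main text of Protocol 4.2.2 recommends removing tissue with spoon-shaped forceps under direct vision. It adds that "hysteroscopic electrocautery is not recommended" and that "Suction and curettage methods should be avoided".

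Note 1 in the same section repeats the cold-knife recommendation and then opens the choice: "Research institutions may choose ultrasound-guided curettage, micro-cold knife technique , intrauterine tissue excision system , or electrosurgical resection, depending on their own conditions". It asks hospitals to record the method and instruments used. The list of surgical data in 5.4 covers date, uterine depth, tissue location and size, operating time, blood loss, distension fluid and complications. It contains neither method nor instruments.

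The background, before II. Research Objectives, compares electrocautery with cold knife and reports that "the latter reduced the incidence of intrauterine adhesions by 90% after surgery". It also gives an adhesion incidence of about 29.6% after curettage.

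Adhesion incidence is the main indicator (6.1). Groups are formed by the treatment that patients choose with their physicians' guidance (IV.2 Grouping). For count data, section 8 names the chi-square or Fisher test and no adjustment or stratification.

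**The concern.** Two hospitals can read 4.2.2 differently and both be following it. Section 9.2 relies on a unified protocol at all sites to control bias, and on surgical method there is no single instruction to follow.

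The comparison is not randomised, so this affects the primary result. By the protocol's own account, method bears on adhesions. The choice between active surgery and expectant management is made with local physicians, so the split may differ between hospitals, and so may the instruments. The text also differs slightly by group: 4.1.2 repeats the cold-knife recommendation for expectant patients, while 4.1.1 names no instrument for active patients, although 4.2.2 recommends cold knife for everyone.

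If method and split vary together, a difference caused by instruments would be reported as an effect of timing. If the case report form is built from 5.4, the variable needed to detect this could be missing.

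**Working it through.** **1. The plan's own figure.** Inputs from IV.3: 5.38% (expectant), 14.29% (active), type I error 0.05, power 90%. Assumed, because not stated: two-sided test, equal groups.

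n per group = (1.960 + 1.282)² × [0.0538 × 0.9462 + 0.1429 × 0.8571] / (0.1429 − 0.0538)² = 10.507 × 0.17339 / 0.007939 = 229.5, so 230 per group and 460 in total. With 20% dropout, 230 / 0.8 = 287.5, so 288 per group and 576 in total. Both stated figures reproduce.

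**2. The planned contrast.** The difference is 14.29 − 5.38 = 8.91 points; the ratio is 14.29 / 5.38 = 2.66.

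**3. What method mix alone could do.** Suppose timing has no effect. Let c be the cold-knife adhesion rate, R the ratio of electrosurgery to cold knife, and f the share of a group operated on by electrosurgery. All other patients are given the rate c, which is a simplification. Then

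group rate = c × [1 + (R − 1) × f].

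A 90% reduction means R = 1 / (1 − 0.90) = 10. Solving for the planned rates, f = (rate / c − 1) / 9:

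| c | Electrosurgery rate 10c | f, expectant | f, active | Gap (points) |
|---|---|---|---|---|
| 5.38% | 53.8% | 0% | 18.4% | 18 |
| 3% | 30% | 8.8% | 41.8% | 33 |
| 2.96% | 29.6% | 9.1% | 42.5% | 33 |
| 2% | 20% | 18.8% | 68.3% | 50 |
| 1.43% | 14.3% | 30.7% | 100% | 69 |

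The first and last rows are the limits, since f cannot go below 0% or above 100%. The 29.6% row borrows the curettage figure as an assumed electrosurgery rate.

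**4. Smaller ratios.** With no electrosurgery in the expectant group, f in the active group = (2.656 − 1) / (R − 1). This is 41% for R = 5 and 83% for R = 3. For R below 2.66 it exceeds 100%, so method mix alone could not produce the planned contrast.

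**5. Smaller imbalances.** With c = 3%, R = 10 and electrosurgery in 10% versus 30%, the rates are 0.03 × 1.9 = 5.7% and 0.03 × 3.7 = 11.1%. With 230 per group, the unadjusted two-sided test is significant about 55% of the time with no true effect of timing.

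**6. Choice at hospital level, as Note 1 describes it.** Take 120 patients at the lead hospital, all cold knife, and 480 elsewhere, half of them operated on by electrosurgery in both groups. If every hospital has the same active/expectant split, the bias is zero. If 80% are expectant at the lead hospital and 40% elsewhere (assumed):

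- Expectant: 96 + 192 = 288 patients, electrosurgery in 96 / 288 = 33.3%.
- Active: 24 + 288 = 312 patients, electrosurgery in 144 / 312 = 46.2%.
- With c = 2% and R = 10, the rates are 8.0% and 10.3%, a spurious difference of 2.3 points. With c = 3% they are 12.0% and 15.5%, or 3.5 points.

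**The case against.** A reader might infer that method carries a tenfold adhesion risk, for curettage as well as electrosurgery, and will generate the whole planned effect. The documents do not support that, for four reasons.

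- The 90% figure compares electrocautery with cold knife only. The title of the cited study names septum, adhesions and submucosal fibroids, not retained products. No such ratio is given for curettage.
- The smallest gap, 18 points, treats 5.38% as a pure cold-knife rate, but IV.3 gives no method mix. It implies 53.8% adhesions after electrosurgery, above the 29.6% after curettage and 40% after repeat curettage in the background.
- Note 1 gives the choice to the institution, not by treatment group. Under that rule, none versus 18.4% would need hospitals using electrosurgery to have no expectant patients. The choice of strategy also follows the patient's wishes. No imbalance is shown.
- For electrosurgery, a recommendation with a permitted local exception is a fair reading, especially in a study that says it does not interfere with treatment.

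It can also be said that method is to be recorded under 4.2.2, that surgeons are trained to a common standard, and that an analysis plan, not shown here, may add stratification.

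All of this limits the size of the concern. It does not remove the clash over curettage or the omission from 5.4, and no analysis plan can reconcile two surgical instructions.

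**Conclusion.** The point stands as an internal contradiction with a plausible but unquantified route to bias. The two parts of 4.2.2 conflict, directly on curettage and more mildly on electrosurgery. The data list in 5.4 does not carry a variable that 4.2.2 asks for. The analysis named in section 8 would not separate method from timing.

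Bias arises only if method and the active/expectant split vary together across hospitals, or if surgeons choose method differently by group within a hospital. Under an assumed tenfold ratio for electrosurgery, a gap in use of about 18 to 69 points could reproduce the full 8.91-point planned difference, about 33 points if the electrosurgery rate is 29.6%. Below a 2.66-fold ratio, method mix alone could not. Smaller imbalances can still distort the test. These are scenarios, not estimates. The sponsor should make the correction, but the material does not show that the planned effect is an artefact of method.

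**What to change.** 1. Reconcile the main text of 4.2.2 with Note 1 so that hospitals read one instruction. Which method is right is for the sponsor.
2. Add surgical method and instruments to 5.4 and the case report form.
3. Record each hospital's usual method before enrolment starts there. For hospitals already enrolling, document it without reference to outcomes.
4. Report method by treatment group and by hospital.
5. Stratify the primary adhesion comparison by hospital or by its usual method, for example with Mantel-Haenszel, and do not rely on the unadjusted chi-square alone. The usual method is a safer stratifier than the method actually used, which may depend on tissue size or bleeding after the strategy was chosen and so be a consequence of it.

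A rule that each hospital must use one method in both groups is not proposed: it would prescribe practice in a study that says it does not interfere with treatment.

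The cost is one clarification, one site declaration, two form fields and a stratified analysis. The downside is small strata. A non-lead hospital averages 40 patients; at the mean planned rate of (5.38 + 14.29) / 2 = 9.8%, that is about 4 adhesion events before dropout, assuming equal groups. A hospital whose patients all choose the same strategy contributes nothing to a hospital-stratified comparison. Stratifying by usual method gives fewer, larger strata, but they too may be thin where few hospitals use the less common methods. Neither stratification removes bias from surgeons choosing method by group within a hospital; the report of method by group and hospital would at least show it.

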4.2.3 Postoperative management

Prevention of intrauterine adhesions: 1) **Inject sodium hyaluronate gel (Gongankang or Yishukang)** into the uterine cavity according to the uterine depth (2-3 ml for a uterine depth of 7 or 8 cm , 5 ml for a uterine depth of 10 cm). 2) If necessary, leave the uterine balloon in place for 48-72 hours and remove it. If there are adhesions in the lower segment of the uterine cavity, part of the internal cervical os, or complete adhesions, handle them according to the intraoperative situation; adjust the amount of water injected into the balloon according to the uterine depth (3 ml for a uterine depth of 7-8 cm, 3.5 ml for a uterine depth of 9 cm, and 4 ml for a uterine depth of 10 cm) . 3) If there are no contraindications, administer 2 mg BID of estradiol valerate (or an equivalent dose of estradiol) orally for 21-28 days postoperatively. (For patients with serum β -HCG levels not typically associated with pregnancy, oral administration until 21 days post-surgery; for patients with β -HCG levels above 100 mmol /L, oral administration until 28 days post-surgery). For the following 6 days, add progesterone (or dydrogesterone) 200 mg orally before bedtime. Continue for a total of two menstrual cycles. Adjustments may be made based on the condition of patients with other intrauterine diseases.

Treatment to promote uterine contraction: routine intravenous administration of uterine contraction agents (ostomycin is routinely used, and ergonovine may be used if necessary) for 48 hours after surgery; oral administration of uterine contraction-promoting drugs (such as *Acanthopanax senticosus* capsules, etc.) for 2 weeks.

Infection prevention: If there are signs of infection or high-risk factors for infection, antibiotics may be used as appropriate, and the type of antibiotic, route of administration, dosage, frequency and duration of administration should be recorded accurately.

Pathological examination: The pregnancy tissue removed during the operation is routinely sent for pathological examination. If endometritis is suspected, endometrial tissue can be sent for immunohistochemical examination of CD138. CNVs can be performed if genetic testing is required.

Postoperative follow-up indicators: β -HCG on the 3rd day after surgery (once a week thereafter until normal), complete blood count (days 1 and 3), CRP, procalcitonin (not mandatory); if necessary, transvaginal ultrasound on the 2nd-3rd day after surgery. A 4D ultrasound is performed on days 16-24 of the third menstrual period after surgery to assess the uterine cavity and blood flow (report templates are available, mainly assessing damage to the endometrium).

Management of retained products of conception after surgery: If ultrasound shows that the diameter of the retained products of conception is less than 0.5 cm, an artificial cycle is given, and a follow-up color Doppler ultrasound and β -HCG test are performed after the next menstrual period to determine whether further surgery is needed; if ultrasound shows that the diameter of the retained products of conception is greater than 0.5 cm, the patient is put back into the expectant management process and managed as an outpatient.

